#### 4.6.2 Secondary outcomes

The secondary outcomes are:

- reasons given by supervisor and colleagues of former sew-ers (separately) for workers no longer being employed at Shahi
- proportions of sew-ers who state they are satisfied or very satisfied with work, feel valued or very valued at work, and are likely or very likely to stay with current employer
- change in self-assessed productivity
- self-report of having been approached by their assigned Captain and/or a supervisor
- change in attitude towards eye health, glasses wear and uptake of eyecare services
- changes in skill grade and associated change in wage
- adherence with spectacle wear
- Quality of Life using the THRIVE Near Vision Quality of Life tool.
- intervention cost-effectiveness

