#### 4.8 Sample size & power

Previous retention trials in this setting have showed 18-20% of overall likelihood of attrition at 5 months follow-up, 50% overall likelihood of attrition at 12 months, 60% at 18 months, 70% at 24 months. Assuming a work retention rate of 50% at 1 year and 40% at 18 months in the Control group, we anticipate that our glasses intervention will increase retention by 20% in the Intervention group at 1 year (hazard of 0.8). Data analysis using a Cox proportional hazard model with 2-sided significance at the 5% level and 80% power yields a total sample size of 1,260 (630 in each group). No correction for attrition is required as attrition is the outcome and therefore no attrition from the sample is possible.

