### 4.10.2 Data collection during trial

Wage and employment status data will be collected on a daily basis from Shahi's Human Resource division. Employment status data will be assessed on a weekly basis over the 18-month intervention period. Intervention costs will be collected by VisionSpring and assessed at the end of the trial intervention period. Secondary outcome data will be collected using the following data collection forms

- Baseline Assessment (following eye examination)
- Endline Assessment (at the end of the 18-month intervention period)
- Spectacle Wear Compliance (on a weekly basis over the 18-month intervention period)
- Self-assessment of productivity by workers enrolled in the trial (once at the start and at the end of the study)
- Supervisor assessment of worker productivity for workers enrolled in the trial (once at the start and at the end of the study)
- Identification of trial participants leaving the employ of Shahi will occur every two months and telephone interviews will be scheduled in two phases (7 months and 16 months after the start of assessment period)

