## CONSORT Flow Diagram

## 8.2 Baseline comparability of randomised groups

Participants in randomised groups will be described separately with respect to the following characteristics at trial entry:

- age
- sex
- education level
- marital status
- number of children and dependants
- median wage compared to urban Bangalore and urban India
- near vision quality of life (THRIVE tool)
- uncorrected visual acuity in each eye separately at distance and both eyes together at near
- urban or rural factory

- mean power of near correction required
- baseline work productivity
- worker self-efficacy
- attitudes towards vision correction
- access to local eyecare services
- history of uptake of eyecare services

Numbers (with percentages) for binary and categorical variables and means (and standard deviations), or medians (with lower and upper quartiles) for continuous variables will be presented; there will be no tests of statistical significance performed nor confidence intervals calculated for differences between randomised groups on any baseline variable.

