## **9. COMPARATIVE ANALYSES**

### **9.1 Analysis of primary and secondary outcomes**

We will calculate the Cox proportional hazard ratio for the rate of retention between Treatment and Control groups with and without adjustment for the following co-variates: age, work tenure, spectacle wear compliance, self-reported self-efficacy, rural vs urban factory, hostel vs non hostel residence, marital and parental status, skill grade (if not too highly colinear with work tenure), work attendance. Linear regression analyses will be performed on potential determinants of primary and secondary outcomes. The study group and all significant variables with p values less than 0.20 in simple regression analyses will be included in multiple regression models. Histograms, normal quantile plots (QQ Plot), and the Shapiro-Wilk normality test will be used to test the normality assumption in regression models. For the Visual Quality of Life (THRIVE) tool, a composite score (eleven items) and near activities sub-score (five items) will be created on 0–100 scales. Intervention costs will comprise the screening test, glasses (and any replacement thereof) as well as direct and indirect costs to the company for facilitating workplace-based sight tests. We will report cost effectiveness distinguishing between study costs and program costs.

The analysis of primary and secondary outcomes will be adjusted for the minimisation factors (age, work tenure at the textile factory, efficiency during baseline assessment) to

account for the correlation between treatment groups introduced by balancing the randomisation. Both the crude unadjusted and adjusted estimates will be presented, but the primary inference will be based on the adjusted analysis.

For multiple imputation of missing data in assessing primary outcomes we will create 20 copies of the data, in which missing values shall be imputed by chained equations, and the datasets will be averaged.

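### Section 9.1 does not specify adjusting secondary outcomes for their own baseline values, although most are collected, so precision is given away

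*SAP*

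**What the plan says.** **Adjustment.** SAP section 9.1: "The analysis of primary and secondary outcomes will be adjusted for the minimisation factors". The factors are age, work tenure and efficiency at the baseline assessment. Crude and adjusted estimates are both to be shown, with the primary inference resting on the adjusted one. The longer covariate list at the start of 9.1 is attached to the Cox model for retention. Table 1 in section 9.3 adds only age, sex and rural or urban site.

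**Outcome definitions.** Section 4.6.2 defines three secondary outcomes as changes: "change in self-assessed productivity", attitudes to eye health and eyecare, and skill grade with its associated wage. THRIVE is listed without saying whether the change or the endline score is analysed. Section 9.1 describes only how its two scores are built.

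**Baseline data.** Section 4.10.2 schedules "Self-assessment of productivity by workers enrolled in the trial (once at the start and at the end of the study") and takes wage daily from factory records. Section 8.2 lists "near vision quality of life (THRIVE tool") and attitudes towards vision correction among the trial-entry characteristics. Skill grade has no named baseline form, but it is a Cox covariate in 9.1 and a subgroup factor in 9.2, so it appears to be held.

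**Other route.** Section 9.1 also plans regressions on unnamed potential determinants, carrying forward those with p below 0.20 in simple regression.

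**The concern.** When an outcome is measured at baseline and endline, regressing the endline value on arm and baseline is at least as precise as comparing raw changes or endline values alone, and usually clearly better. The set fixed in 9.1 leaves that covariate out. Baseline efficiency is related to some of these outcomes, but it is not the baseline value of any of them.

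Precision matters here because the trial is sized for retention only and the SAP states no power for any secondary outcome. By its own retention assumptions, more than half of each arm may have left by 18 months. A raw change is also sensitive to a chance imbalance at baseline, through regression to the mean.

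**Working it through.** **The plan's own figure.** Section 4.8 uses "2-sided significance at the 5% level and 80% power" with a hazard ratio of 0.8 and "yields a total sample size of 1,260 (630 in each group"). Schoenfeld's formula gives 4 × (1.960 + 0.842)² / (ln 0.8)² = 631 events. Dividing by 0.50, the one-year control event rate applied to both arms, gives 1,262 against 1,260 stated. The SAP does not show its route, but the figure is reproduced. It concerns the primary outcome and does not change under this point.

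**Relative variance of the arm effect.** Take equal SDs at baseline and endline, correlation r between them, and no other covariates:

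- final score alone: 1
- raw change: 2(1 − r)
- endline adjusted for baseline: 1 − r²

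The SAP does not give r, so 0.3 to 0.7 is an assumption.

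| r | Raw change | Baseline-adjusted | Reduction v change | Reduction v final score |
|---|---|---|---|---|
| 0.3 | 1.40 | 0.91 | 35% | 9% |
| 0.5 | 1.00 | 0.75 | 25% | 25% |
| 0.7 | 0.60 | 0.51 | 15% | 49% |

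**Illustration on retained workers.** Section 4.8 reads: "Assuming a work retention rate of 50% at 1 year and 40% at 18 months in the Control group". Control: 630 × 0.40 = 252. Intervention, with hazard ratio 0.8 and proportional hazards: 630 × 0.4^0.8 = 630 × 0.480 = 303. That endline is measured only in workers still employed is an assumption.

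The standard error in SD units is √(1/252 + 1/303) = 0.0853, multiplied by the square root of the relative variance. The difference detectable with 80% power is 2.8016 × SE. Power for a true 0.2 SD (assumed) is Φ(0.2/SE − 1.96).

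| r | Detectable SD: change / final / adjusted | Power at 0.2 SD: change / final / adjusted |
|---|---|---|
| 0.3 | 0.283 / 0.239 / 0.228 | 51% / 65% / 69% |
| 0.5 | 0.239 / 0.239 / 0.207 | 65% / 65% / 77% |
| 0.7 | 0.185 / 0.239 / 0.171 | 86% / 65% / 91% |

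At r = 0.5 the 95% interval half-width falls from 0.167 to 0.145 SD.

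**If every randomised worker were measured.** SE = √(2/630) = 0.0563. At r = 0.5, power for 0.2 SD is Φ(3.55 − 1.96) = 94% unadjusted and Φ(3.55/√0.75 − 1.96) = 98% adjusted. The proportional cut in variance is the same, but the gain in power is small.

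**The case against.** **The p<0.20 screen may already do the job.** With about 555 workers, a baseline score correlated 0.3 with endline gives t = 0.3 × √553 / √0.91 = 7.4. Against the change, its correlation is −√((1 − r)/2), or −0.59, −0.50 and −0.39 at r = 0.3, 0.5 and 0.7. Any baseline offered to the screen would almost certainly enter, and regressing the change on arm plus baseline gives the same arm effect as regressing the endline value on both. This has force. But 9.1 does not list the candidates and does not tie the screened model to the one that carries the inference. Section 9.3 itself warns that choosing confounders by preliminary tests distorts error rates. The screen makes the loss uncertain; it does not remove it.

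**The SAP does not commit to an unadjusted THRIVE score or to raw changes.** A reader might infer that it fixes such analyses. It does not: THRIVE is left open, and own-baseline adjustment is unspecified, not ruled out. The point is therefore one of omission.

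**Bias.** A reader might infer that raw changes give biased effects. Over randomisation they do not. The sensitivity is conditional on a chance imbalance in the sample at hand.

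**The comparator is too favourable to the point.** The formulas describe models without covariates, whereas 9.1 already adjusts for age, tenure and baseline efficiency. Where efficiency explains variance in productivity, skill grade or wage, the true gain is smaller by an amount the SAP cannot settle. Very high correlations also shrink the gain against a raw change: at r = 0.9 it is 1 − (1 + 0.9)/2 = 5%. The SD formulas do not carry over directly to ordinal or categorical items. All of this stands.

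**The retained sample.** Section 8.3 expects minimal loss for secondary outcomes, so 252 v 303 is not the SAP's figure for endline. If it is right, the groups compared are selected on the primary outcome, and baseline adjustment does not cure that selection.

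**Conclusion.** The point holds as an omission that costs precision in secondary outcomes. Section 9.1 fixes the covariates behind the inference and leaves out the outcome's own baseline, and no other provision guarantees it.

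The variance reduction of 15-35% against raw change and 9-49% against final score rests on r between 0.3 and 0.7, equal SDs and no other covariates. It is best read as the upper end for outcomes related to baseline efficiency. The rise in power from 65% to 77% rests further on r = 0.5, a 0.2 SD difference and endline measurement in retained workers only.

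The primary result and the sample size of 1,260 are not touched. The documents do not support calling this a source of systematic bias.

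**What to change.** Add to section 9.1:

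- Each continuous secondary outcome with a baseline measurement (THRIVE scores, self-assessed productivity, wage, attitude scores) is analysed as its endline value by linear regression on arm, its own baseline value and the adjustment factors already in 9.1 (age, work tenure, baseline efficiency). The result reported is the adjusted difference at endline.
- Skill grade is analysed with an ordinal model that includes the baseline grade.
- Binary items that are also asked at baseline are analysed with a logistic model that includes the baseline response.
- This is the model that carries the inference, whatever the p<0.20 screen selects.

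This also settles whether THRIVE is analysed as change or endline. The cost is a few sentences and no new data. The downside is negligible: under the complete-case rule in section 8.3 a missing baseline drops a case, and that section expects under 2% missing covariate data. Selection from differential retention needs separate handling in the interpretation.

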## 9.2 Pre-specified subgroup analysis

The consistency of the effect of the intervention across specific subgroups will be assessed using the statistical test of interaction. Note that this study was not designed to have sufficient power to test for interaction terms in these subgroup analyses; we will interpret the results with caution. Pre-specified subgroup analyses include:

- Sex
- Skill grade (<median,  $\geq$ median)
- Degree of Presbyopia (early presbyopia, reading glass powers < 1.25D; moderate presbyopia, 1.25D  $\leq$  reading glasses powers < 2.00D, advanced presbyopia: reading glasses powers  $\geq$ 2.00D)
- Age group (35 to 39 years, 40 to 49 years, 50 years and older)
- Compliance rate observed in the factory (<median,  $\geq$ median)
- Presenting binocular near visual acuity of N8 and worse

Subgroup analysis will be performed on the primary outcome and mean efficiency outcomes.

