## 4.5 Interventions

Eligible participants will be randomly assigned to Intervention or Control Groups (1:1). Intervention group participants will receive free reading glasses after undergoing a vision screening at the factories, which will mark the beginning of the assessment period. In addition to receiving free reading glasses, participants in the Intervention Group will be eligible for free replacement glasses in the event of loss or damage throughout the trial. Control group participants will receive free reading glasses at the end of the assessment period (18 months after the beginning of the assessment period). An interim analysis will be performed by the trial statistician. If the Trial Management Group (TSG) terminates the trial on the recommendation of the trial statistician, then Control Group participants will receive free reading glasses at trial closure. The trial will be investigator-masked, but not participant-masked, because the investigators do not feel provision of zero-power glasses to the control group is ethical. However, participants will have limited knowledge of the study hypothesis, limiting potential placebo effects.

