## 6. ADHERENCE TO THE INTERVENTION

Adherence to the intervention will be assessed through observation of spectacle wear while working. Adherence will be measured surreptitiously on a weekly basis. The enumerators assessing spectacle wear compliance are GBL staff members familiar to Shahi workers but are not revealed to be collecting glasseswear adherence data to ensure minimum modification of compliance behaviour in present of enumerators.

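### The compliance subgroup in SAP section 9.2 is measured after randomisation and not defined for Controls, so at worker level its interaction is either not estimable or not a randomised comparison

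*SAP*

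**What the plan says.** Section 9.2 of the SAP lists "Compliance rate observed in the factory", below the median against at or above it, among the pre-specified subgroups. Consistency of the effect across subgroups "will be assessed using the statistical test of interaction", and "Subgroup analysis will be performed on the primary outcome and mean efficiency outcomes". The primary outcome (section 4.6.1) is time from randomisation to loss of employment. The only caution in section 9.2 is that "this study was not designed to have sufficient power to test for interaction terms in these subgroup analyses".

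Section 6 says how compliance is obtained: "Adherence to the intervention will be assessed through observation of spectacle wear while working", and "Adherence will be measured surreptitiously on a weekly basis". Section 4.10.2 gives the same weekly schedule over the 18-month intervention period. Under section 4.5, "Control group participants will receive free reading glasses at the end of the assessment period". Section 5.2.2 foresees that some Controls will buy glasses elsewhere and keeps them in the intention-to-treat analysis.

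The SAP does not say which arm is observed, how Controls are classified, whose median is used, over which weeks the rate is taken, or whether the rate belongs to a worker or to a factory.

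**The concern.** A subgroup interaction test compares randomised arms within strata that allocation cannot have altered. Sex, age and degree of presbyopia can be fixed at baseline. Compliance cannot: it arises after randomisation, allocation largely determines it, and it is seen only while the worker is still employed, which is the outcome itself. Workers who wear glasses steadily may also be those most attached to the job. Splitting on wear then sorts workers partly by their tendency to stay.

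The power caution does not cover this. Low power means a real interaction may be missed; here the danger is an interaction that is not there. Such a result would carry the standing of a pre-specified analysis. Section 9.3 also brings variables with a significant subgroup result into the sensitivity models for the treatment effect, so a spurious finding could spread.

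**Working it through.** **1. The plan's own figure.** The SAP gives no figure for this subgroup. Its sample size (section 4.8: hazard ratio 0.8, two-sided 5%, 80% power) reproduces. Events = 4(1.960 + 0.842)² / (ln 0.8)² = 4 × 7.849 / 0.0498, or 631. Dividing by the 12-month Control leaving rate of 50%, applied to both arms, gives 631 / 0.5 = 1,262, against the stated 1,260. This is not in dispute.

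**2. Simulation set-up, true hazard ratio 1.**
- From the SAP: 630 workers per arm, 40% retained at 18 months (78 weeks), weekly observation. Weekly hazard λ = −ln(0.4)/78 = 0.0117.
- Assumed: each worker has a standard normal attachment score u. The hazard of leaving is λ·exp(−γu), and the log-odds of wear in any week are 1 + u. The link γ was varied from 0 to 0.5.
- There were 600 trials per setting in steps 3 and 4, and 400 in steps 5 to 7.

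**3. Intervention split at its own median, each half against all Controls, rate over weeks employed.**

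| Link γ | HR, high compliers | HR, low compliers | False benefit in high (nominal 2.5%) | High and low differ (nominal 5%) |
|---|---|---|---|---|
| 0 | 1.01 | 0.99 | 1.3% | 6.8% |
| 0.1 | 0.94 | 1.06 | 12% | 24% |
| 0.25 | 0.84 | 1.18 | 46% | 90% |
| 0.5 | 0.72 | 1.37 | 93% | 100% |

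**4. Same split, rate over all 78 weeks, wear unrelated to leaving.** HR 0.34 in high and 2.68 in low compliers, with false benefit in 100% of trials. Early leavers cannot score high on a fixed denominator.

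**5. Overall median, no Control wears glasses.** The median is about zero, no Intervention worker falls below it, and the interaction was estimable in 0% of trials.

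**6. Overall median, some Controls wear their own glasses, γ = 0.25.**

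| Share of Controls | Control / Intervention at or above median | Control / Intervention below median | HR at or above | HR below | Interaction rejects (nominal 5%) |
|---|---|---|---|---|---|
| 5% | 30 / 601 | 600 / 29 | 0.98 | 2.38 | 76% |
| 10% | 57 / 574 | 573 / 56 | 1.01 | 1.86 | 71% |
| 20% | 106 / 528 | 525 / 102 | 1.00 | 1.51 | 59% |

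The few Intervention workers below the median are selected poor wearers, set against nearly all Controls. The result is apparent harm there, and no apparent benefit above.

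**7. Factory-level rate, factories split at the median.** With 4 or 10 factories (number assumed) and γ of 0.25 or 0.5, hazard ratios were 0.98 to 1.02 and rejection 4.5% to 8.8%. The simulation error of a 5% rate in 400 trials is √(0.05 × 0.95 / 400) = 1.1 points, so 8.8% (10 factories, γ = 0.5) is a little above nominal.

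**8. Intention-to-treat comparison.** In every setting of steps 3 and 4 the unadjusted comparison of the arms gave HR 1.00 and rejected in 4% to 6% of trials. The distortion comes from the split.

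**The case against.** It can be said for the plan that the main inference is by intention to treat, that section 9.2 promises cautious interpretation, and that the simulated biases rest on an assumed link and on classification rules the SAP does not state. All of that is fair. The step 3 percentages belong to one possible reading, with no link that reading has almost no bias, and nothing in the SAP fixes how strong the link is. A true effect of wearing glasses is not excluded either: a larger effect in compliers could come from selection, but need not.

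The factory-level reading is the best defence. The listed item can be read as a factory's rate, and on that reading there is little bias. But the SAP does not say so.

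A reader might go further and infer that compliance exists only for Intervention workers, so that the interaction test will show a false benefit. The SAP does not support this. Section 6 names no arm, section 5.2.2 expects some Controls to acquire glasses, and section 9.1 lists compliance as a covariate in a two-arm Cox model. The inference also defeats itself: a variable absent in Controls leaves no interaction to estimate. When an interaction was actually estimated at worker level (step 6), the distortion was mainly apparent harm.

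What stands is that the variable is measured after randomisation and is undefined for Controls, and that a caution about power answers neither point.

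**Conclusion.** The point holds for a worker-level reading. As written, the compliance interaction is either not estimable (nearly all Controls at zero wear) or not a randomised comparison, and it can mislead in either direction. The size is uncertain. False benefit in high compliers ranged from 12% to 93% of trials for assumed links of 0.1 to 0.5, and false interactions from 76% to 59% with 5% to 20% of Controls wearing their own glasses. That the split lacks the protection of randomisation depends on none of these assumed values. On a factory-level reading the concern is minor.

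The intention-to-treat comparison and the sample size are untouched, so this should be corrected but does not threaten the primary result. Adjustment for compliance in section 9.1 is a separate matter and was not sized here.

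**What to change.** Delete compliance from the subgroup list in section 9.2, and state that it cannot enter the section 9.3 models through a subgroup result. Keep the weekly descriptive report of wear already planned in section 8.4.

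If the effect in wearers is of interest, add a separate analysis labelled secondary or exploratory that uses randomisation as the instrument, for example a complier-average effect. State how wear is defined in each arm, over which weeks, and on what assumptions the estimate rests. If a factory-level rate was intended, say so, name the arm and weeks from which it is computed, and label it exploratory.

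Cost: SAP wording and one optional analysis. The sample size stays at 1,260, and wear is already being recorded weekly; if it is not recorded in Controls, the optional analysis needs a stated assumption about their wear.
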